9.6. Data Management

MS Service-Center database:

The Biogen MS Service-Center provides medical information to German MS patients on request. Furthermore, it offers enrollment to a patient support program for SC Peginterferon beta-1a and IM Interferon beta-1a patients including injection handling training and individual adherence coaching from a personal coach upon medical need. Services have been provided since October 2014 from Audimedes GmbH, certified according to ISO 9001:2015 criteria. Compliance with these criteria is audited annually by an external certified audit organization. Database includes data of about 45,000 patients with MS.

From 2014 until December 2019 3, 615 patients under IM Interferon beta-1a treatment and 7,529 patients under SC Peginterferon beta-1a treatment have been enrolled to the patient support program. In the database, demographics and therapeutic history including adverse events, product complaints and pregnancy reports are captured in real time. All personnel dealing with the patient information and database undergo regular training to ensure quality of information, communication skills and quality of data in the database. All data is pseudonymized and pooled for this analysis.

Study database:

Data collection for the retrospective study part will be performed by extracting the relevant data from the existing MSSC database and importing it into an electronic PDF (ePDF) by a CRO. During the telephone interview, missing data will be completed directly in the ePDF, if appropriate. After the CRO has received all completed ePDFs, all

CONFIDENTIAL

The information contained herein may not be used, disclosed, or published without the written consent of
Biogen MA Inc.

data will be exported and used for analysis by the CRO as well as for updating the MSSC database (Audimedex GmbH).

All relevant data for the prospective study part is documented on standardized patient questionnaires provided as ePDF. The MSSC personnel documents the results of the telephone interview directly in the ePDF and after completion, the ePDF is transferred to the CRO to export and analyze the data together with the retrospective data.

Personal data of patients are gathered, stored and processed exclusively in a pseudonymous form according to national data protection laws.

9.7. Data Analysis

This study is an observational study with focus on existing pregnancy reporting forms (retrospective part) and a patient's questionnaire which is completed at a single point of time (prospective part).

It will not be distinguished between the two treatments, i.e. the data will be pooled for analysis.

All documented data are analyzed by descriptive statistics, that is, no formal statistical hypothesis will be formulated, and no statistical tests will be carried out.

Categorical variables will be summarized descriptively by absolute frequencies and percentages. The denominator for all percentages will be the total number of pregnancies within the respective group, unless otherwise indicated. Percentages will be presented to one decimal place and will not be displayed for zero frequencies. A row denoted "Missing" will be included in all tabulations to clearly indicate the completeness of the collected data, i.e. missing data is included in the denominator of the percentages.

Continuous variables will be tabulated by descriptive statistics, i.e. the total number of pregnancies (n), number of pregnancies with missing values (Nmiss), mean, standard deviation, median, quartiles, minimum and maximum.

If sensible, free text entries will be transferred into appropriate encoding schemes to be analyzed in frequency tables. If appropriate, change of values during/after pregnancy to values before pregnancy will be calculated and analyzed using descriptive statistics or shift tables.

In case of missing or unknown data, no data imputation will be performed. For a complete presentation all obtained data will be listed.

A statistical analysis plan will be drafted and finalized before the end of the overall data collection to describe all analyses in more detail.

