	
questionnaire which is completed at a single point of time (prospective part).
 
It will not be distinguished between the two treatments, i.e. the data will be pooled for analysis. All documented data are analyzed by descriptive statistics, i.e. absolute frequencies and percentages for categorical variables and mean, standard deviation and percentiles for continuous variables. No formal statistical hypothesis will be formulated, and no statistical tests will be carried out.
 
In case of missing or unknown data, no data imputation will be performed.
										
Milestones:	
 
 Start of data collection	December 2020	
 
 (prospective part of the study):		
 
 End of data collection:	31 March 2021	
 
 Registration in EU PAS Register:	October 2020	
 
 Final report of study results:	30 June 2021	
 
	Start of data collection	December 2020	(prospective part of the study):		End of data collection:	31 March 2021	Registration in EU PAS Register:	October 2020	Final report of study results:	30 June 2021
Start of data collection	December 2020										
(prospective part of the study):											
End of data collection:	31 March 2021										
Registration in EU PAS Register:	October 2020										
Final report of study results:	30 June 2021										

CONFIDENTIAL

The information contained herein may not be used, disclosed, or published without the written consent of Biogen MA Inc.

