Peginterferon beta-1a, pegylated interferon beta-1a, was developed as a modern pegylated version of the native protein interferon beta-1a with improved pharmacological properties to provide an interferon with increased interferon efficacy, higher interferon exposure, decreased renal clearance and longer elimination half-life to facilitate adherence by reducing frequency of application. It was approved by the EMA in July 2014 and has been available in Germany since September 2014. Peginterferon beta-1a is injected every 2 weeks. Peginterferon beta-1a hence constitutes an additional option for injectable disease-modifying therapy of RRMS with an established risk-benefit ratio [Calabresi 2014; Arnold 2014; Kieseier 2015; Arnold 2017; Calabresi 2017; Arnold 2018; Newsome 2018], established injectable efficacy [Calabresi 2014; Arnold 2014; Kieseier 2015; Arnold 2017; Calabresi 2017; Arnold 2018; Newsome 2018] and statistically significant lowest total cumulative flu-like symptoms (FLS) duration under the interferons [Hendin 2018]. This might be especially useful in the sensitive period of pregnancy and lactation.

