9.2.3 Covariates and other characteristics? (e.g. age, sex, clinical and drug use history, co-morbidity, co-medications, lifestyle)				9.4.
9.3 Is a coding system described for:				

CONFIDENTIAL

The information contained herein may not be used, disclosed, or published without the written consent of Biogen MA Inc.

Section 9: Data sources	Yes	No	N/A	Section Number
9.3.1 Exposure? (e.g. WHO Drug Dictionary, Anatomical Therapeutic Chemical (ATC) Classification System)				9.7
9.3.2 Outcomes? (e.g. International Classification of Diseases (ICD), Medical Dictionary for Regulatory Activities (MedDRA))				CRF
9.3.3 Covariates and other characteristics?				9.7
9.4 Is a linkage method between data sources described? (e.g. based on a unique identifier or other)				

Comments:

Exposure of study drug does not need any coding, other medication and free text entries will be categorized in analysis programs and outcomes of children are already categorized in the standardized German pediatric check-up booklet.

Section 10: Analysis plan	Yes	No	N/A	Section Number
10.1 Are the statistical methods and the reason for their choice described?				9.5, 9.7
10.2 Is study size and/or statistical precision estimated?				9.5
10.3 Are descriptive analyses included?				9.7
10.4 Are stratified analyses included?				
10.5 Does the plan describe methods for analytic control of confounding?				
10.6 Does the plan describe methods for analytic control of outcome misclassification?				

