10.7 Does the plan describe methods for handling missing data?				9.7
10.8 Are relevant sensitivity analyses described?				

Comments:

PAS study with one pooled treatment

Section 11: Data management and quality control	Yes	No	N/A	Section Number
11.1 Does the protocol provide information on data storage? (e.g. software and IT environment, database maintenance and anti-fraud protection, archiving)				9.6
11.2 Are methods of quality assurance described?				9.6
11.3 Is there a system in place for independent review of study results?				9.8

CONFIDENTIAL

The information contained herein may not be used, disclosed, or published without the written consent of Biogen MA Inc.

Comments:

--

Section 12: Limitations	Yes	No	N/A	Section Number
12.1 Does the protocol discuss the impact on the study results of: 12.1.1 Selection bias? 12.1.2 Information bias? 12.1.3 Residual/unmeasured confounding? (e.g. anticipated direction and magnitude of such biases, validation sub-study, use of validation and external data, analytical methods)				9.9
				
				
12.2 Does the protocol discuss study feasibility? (e.g. study size, anticipated exposure uptake, duration of follow-up in a cohort study, patient recruitment, precision of the estimates)				9.2.3.1

Comments:

--

Section 13: Ethical/data protection issues	Yes	No	N/A	Section Number
13.1 Have requirements of Ethics Committee/ Institutional Review Board been described?				10.1
13.2 Has any outcome of an ethical review procedure been addressed?				10.1

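### Section 9.7 pools SC peginterferon beta-1a with IM interferon beta-1a and plans no table by product, so a product-specific excess in a common pregnancy outcome would be diluted

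*Protocol*

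**What the plan says.** Section 9.7 fixes the rule for both products: "It will not be distinguished between the two treatments, i.e. the data will be pooled for analysis". The abstract says the same. The ENCePP checklist in Annex 2 repeats it in its comments on exposure and on the analysis plan, the latter reading "PAS study with one pooled treatment".

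The analysis is descriptive: "no formal statistical hypothesis will be formulated, and no statistical tests will be carried out". For the primary endpoints this means: "Categorical variables will be summarized descriptively by absolute frequencies and percentages".

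Section 9.7.2 evaluates the primary endpoint in three subgroups: treatment continued before and during pregnancy, paused or stopped during pregnancy, and started during pregnancy. None is by product. Section 9.5 nevertheless counts pregnancies by product, and section 9.4.1 extracts use of either product from the service-center database. Section 7 describes the pegylated product as developed to give, among other properties, "higher interferon exposure, decreased renal clearance and longer elimination half-life". Section 9.9 names the missing reference therapy as a limitation but not the pooling.

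**The concern.** The primary objective (8.2) is the impact of exposure to either product on pregnancy outcome. The two products have separate marketing authorisations, and by the protocol's own account they differ in the exposure they give. The eligible populations differ too, because 9.2.1 admits CIS for interferon beta-1a only. A pooled percentage is an average of two product-specific percentages, weighted by how many reports each happens to contribute. If one product carried an excess, the average would show only part of it and could not say where it came from.

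This is not a detail that can simply wait for the SAP. Section 9.7 says the SAP will describe the analyses more fully, but a SAP that added a split by product would contradict a rule the protocol has already set.

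**Working it through.** **Inputs**
- Section 9.5: 202 pregnancies in 184 women (SC), 245 in 199 women (IM), 368 live births, 80% return.
- Section 7.1.2, European registry: spontaneous abortion 10.7% against up to 21% in the general population; live births with congenital anomalies 1.8% against 2.1-4.1%.
- Assumption, not from the documents: the SC rate is twice the IM rate. The protocol gives no outcome by product.

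**The plan's own figure.** 368 x 0.80 = 294.4, which agrees with the roughly 290 questionnaires in 9.5. Totals: 202 + 245 = 447 pregnancies; 184 + 199 = 383 women. Section 9.5 states no precision or power to reproduce.

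**Dilution.** Pooled rate = w x p(SC) + (1 - w) x p(IM), with w = 202/447 = 0.452. An excess confined to SC therefore enters the pooled rate at 45% of its size.

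**Common outcome, doubled on SC.** p(IM) = 10.7% and p(SC) = 21.4%. Expected counts: 202 x 0.214 = 43.2, taken as 43; 245 x 0.107 = 26.2, taken as 26. Intervals are exact (Clopper-Pearson), two-sided 95%.

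| Column | Count | % | 95% CI |
|---|---|---|---|
| SC | 43/202 | 21.3 | 15.9-27.6 |
| IM | 26/245 | 10.6 | 7.1-15.2 |
| Pooled | 69/447 | 15.4 | 12.2-19.1 |

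The pooled figure, with its whole interval, lies below 21%. It is above the registry's 10.7%, so a careful reader would notice some elevation, but the table would not show that it came from one product. In two columns the contrast is plain: the intervals do not overlap.

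**Rare outcome, doubled on SC.** Start from 1.8%, a rate for live births that is applied here to all pregnancies because live births by product are not given. The counts are 7/202 (3.5%, 1.4-7.0) and 4/245 (1.6%, 0.45-4.1), pooled 11/447 (2.5%, 1.2-4.4). Here the columns overlap heavily.

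**What the columns could separate.** No test is proposed. As a gauge only, a two-sided 5% comparison of two proportions (normal approximation) would have about 87% power for the doubled spontaneous abortion rate, about 23% for a doubling from 1.8% and about 55% for a tripling.

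**Zero events.** The upper 95% limit is 1 - 0.025^(1/n): 1.8% for 0/202, 1.5% for 0/245 and 0.8% for 0/447.

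**The case against.** Pooling is a disclosed choice, stated the same way throughout, so there is no internal contradiction. The study supplements interferon beta registries that report on the class, and the 2019 label change in 7.1.2 covers the class, both products included. Section 7 describes pharmacology and claims no difference in pregnancy risk. No figure in the protocol suggests that the products differ in outcome. All this stands, and it supports keeping the pooled result as the main one. It does not explain why the split is ruled out when the product is on record.

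Several stronger readings are tempting and are not supported:
- *The primary result is a single percentage.* It is not: 9.1.1 lists seven outcomes and 9.7.2 gives three exposure subgroups.
- *A product signal could never be found.* Section 9.7 also lists all obtained data, although it does not say whether the listings identify the product. The defect is in the planned tables.
- *Zero events are hidden.* The rule reads "Percentages will be presented to one decimal place and will not be displayed for zero frequencies". Only the percentage is blank; the count of 0 and the denominator remain. This is presentation.
- *Confidence intervals and an allowance for repeat pregnancies are wrongly left out.* The protocol excludes tests, not intervals, and both matters commonly go to the SAP, which was not available for this review.
- *The checklist wrongly claims precision.* The item reads "10.2 Is study size and/or statistical precision estimated", and 9.5 does estimate study size, so the tick is correct.
- *Pooling would mask an anomaly signal that a split would reveal.* The calculation does not bear this out. A doubled SC rate of 3.5% is itself inside the 2.1-4.1% background range, and the product intervals overlap.

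**Conclusion.** The point holds in a limited form. The protocol rules out a breakdown by product and plans none, although it records the product and itself describes a pharmacological difference. For a common outcome the consequence is material: a doubling on SC from 10.7% would appear as 15.4% pooled, under the population figure of up to 21%, with nothing in the tables to locate it. For rare outcomes a split would inform little.

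The size rests on an assumed doubling and on the mid-July 2020 counts, which may grow until the cut-off. The intervals treat pregnancies as independent; 447 come from 383 women, so they are probably slightly too narrow. The SC figure of 21.3% is only just above 21%, and its interval includes 21%; the excess shows against the IM column and the registry rate, not clearly against the population figure. A difference between columns would not by itself be causal, since the users of the two products may differ. The documents do not support inferring that such a difference exists, or that the sponsor's pooled result is invalid.

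**What to change.** Amend 9.7, with matching changes in the abstract and the Annex 2 comments:
- Keep the pooled column as the main result.
- Add one descriptive column per product for the primary endpoints, preferably with exact 95% confidence intervals.
- State that no between-product test will be done, which keeps the change consistent with the descriptive aim.
- In 9.9, name pooling as a limitation, together with the low ability to separate the products on rare outcomes.

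Printing 0.0% with an upper limit, and a check restricted to each woman's first pregnancy, are optional and can be settled in the SAP.

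The cost is extra table columns and programming, with no new data. The by-product intervals will be wide, and the text should warn against reading differences in rare outcomes as evidence for or against either product.

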9.7.1. Analysis Population

9.7.1.1. Primary Endpoint Analysis

The analysis set for the primary objective will be defined by the group of patients that are registered in the PSP, agreed to the privacy policy of the registration form, and were

CONFIDENTIAL

The information contained herein may not be used, disclosed, or published without the written consent of
Biogen MA Inc.

eligible to participate in this observation (see 9.2.1 **Fehler! Verweisquelle konnte nicht gefunden werden.**).

9.7.1.2. Secondary Endpoint Analysis

The analysis set for the secondary objectives will be defined by the group of patients that gave written informed consent, had a live birth outcome, provided data for the patient questionnaire and were eligible to participate in this observation (see 9.2.1 **Fehler! Verweisquelle konnte nicht gefunden werden.**).

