	
 • Data on newborn (sex, weight, height, head circumference, Apgar scores) • Weight, height and head circumference of child measured under statutory programs of the standardized German pediatric check-up booklet • Abnormalities diagnosed during pediatric check-ups under statutory programs as reported in the standardized German pediatric check-up booklet • Pregnancy and family anamnesis • Vitamin K prophylaxis • Body weight, height, head circumference of the child as documented for check-ups 2-8 • Lactation (exclusive breastfeeding and breastfeeding with supplemental feedings) • Other MS therapies during or after pregnancy and start relative to birth • MS relapses in the year before pregnancy • MS relapses during pregnancy • MS relapses after pregnancy/birth • EDSS before, during and after pregnancy

Data Sources:
	
Retrospective Data Capture: MSSC database, i.e. the entered pregnancy report (to be completed as soon as pregnancy becomes known) and pregnancy outcomes report (to be completed after completion of pregnancy).
 
Prospective Data Capture Standardized ePDF questionnaire completed during telephone interview

Study Size:
	
Since this is an exploratory study and no formal hypothesis-testing will be carried out, there is no formal sample size calculation. The sample size of the prospective study part depends on how many patients are eligible to participate in this observation and will agree to provide data for the questionnaire. Based on the current data entered in the MSSC data base, about 310 patient questionnaires are expected to be completed during the telephone interview. It is expected that about 400 patients will be included in the retrospective study part.

Data Analysis:
	
This study is an observational study with focus on existing pregnancy reporting forms (retrospective part) and a patient's

CONFIDENTIAL

The information contained herein may not be used, disclosed, or published without the written consent of Biogen MA Inc.

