9.1.2. Secondary Endpoints

- Average weight, average length, and average head circumference of the children from birth to 48 months
- Number and proportion of abnormalities diagnosed during pediatric check-ups under statutory programs in Germany and reported in the standardized German pediatric check-up booklet “Kinderuntersuchungsheft” (data on check-ups 1-8 will be collected covering the first 46 - 48 months of life). Refer to Annex 3 for recommended timepoints and details on the examinations.
- Number and proportion of women discontinuing SC Peginterferon beta-1a or IM Interferon beta-1a therapy during pregnancy and time to discontinuation in relation to beginning of pregnancy

CONFIDENTIAL

The information contained herein may not be used, disclosed, or published without the written consent of Biogen MA Inc.

- Number and proportion of women starting SC Peginterferon beta-1a or IM Interferon beta-1a therapy during pregnancy and time to start in relation to beginning of pregnancy
- Number and proportion of women restarting SC Peginterferon beta-1a or IM Interferon beta-1a therapy after birth and time to restart in relation to birth
- Number and proportion of women starting another MS therapy during/after pregnancy and time to start in relation to birth
- Number and proportion of women using other therapies during pregnancy (categorized by Paracetamol, other therapies for the alleviation of FLS), folic acid, medication for depression, corticosteroids, adrenocorticotrophic hormone, other therapies)
- Number and proportion of MS relapses in women with SC Peginterferon beta-1a or IM Interferon beta-1a therapy before, during and after pregnancy
- Change of EDSS during and after pregnancy to EDSS before pregnancy
- Lactation: number of women breastfeeding under SC Peginterferon beta-1a or IM Interferon beta-1a therapy and duration of SC Peginterferon beta-1a or IM Interferon beta-1a exposed breastfeeding
- Time to first MS relapse after introduction of the first supplemental feedings in women with SC Peginterferon beta-1a or IM Interferon beta-1a therapy during lactation

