9.4. Data Sources

9.4.1. Retrospective Data Capture

Main data source for the retrospective data capture is the MSSC database, i.e. the entered pregnancy report (to be completed as soon as pregnancy becomes known) and pregnancy outcomes report (to be completed after completion of pregnancy).

The following data is extracted from the MSSC database:

- Demographic data (age, height, weight)
- SC Peginterferon beta-1a or IM Interferon beta-1a use, including treatment duration, prior to, during and after pregnancy
- Concomitant medication prior to and during pregnancy
- Pregnancy outcome (live birth without defect, live birth with defects, ectopic pregnancy, spontaneous abortion, elective termination of pregnancy, preterm birth, stillbirth), including gestation week and description of abnormalities of the fetus, reason for termination, diagnostics, etc.
- Complications during pregnancy

CONFIDENTIAL

The information contained herein may not be used, disclosed, or published without the written consent of Biogen MA Inc.

- Type of delivery (vaginal delivery: spontaneous, induced, instrumentally supported; Caesarean section: elective, medically indicated), complications during delivery or reasons for an intervention
- Placenta normal/abnormal
- Data on newborn (sex, weight, height, head circumference, Apgar 1 minute, Apgar 5 minutes, Apgar 10 minutes)

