9.5. Study Size

Since this is an exploratory study and no formal hypothesis-testing will be carried out, there is no formal sample size calculation. The sample size of this study depends on how many patients are eligible to participate in this observation and will agree to provide data for the questionnaire.

As of mid-July 2020, there were n = 202 pregnancy and pregnancy outcome reports for 184 female patients under SC Peginterferon beta-1a and n = 245 pregnancy and pregnancy outcome reports for 199 female patients treated with IM Interferon beta-1a in the MSSC database. The outcome of 368 pregnancies was a live birth, hence qualify for the prospective study part. About 290 patient questionnaires are expected to be completed during the telephone interview (80% return rate estimated). This number might increase until 15th October 2020 - the cut-off point for data collection.

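### Secondary endpoints held in the database are tabulated only for live-birth mothers who complete the interview, leaving out up to 21% of live births or 35% of pregnancies

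*Protocol*

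**What the plan says.** Section 9.7.1.2 fixes one set for all secondary objectives: "defined by the group of patients that gave written informed consent, had a live birth outcome, provided data for the patient questionnaire", subject to general eligibility. Section 8.3 and the Abstract carry the same limit, and no secondary endpoint is exempted.

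The data sources do not follow that line. The database extract in section 9.4.1 includes "SC Peginterferon beta-1a or IM Interferon beta-1a use, including treatment duration, prior to, during and after pregnancy", concomitant medication, and "Data on newborn (sex, weight, height, head circumference, Apgar 1 minute, Apgar 5 minutes, Apgar 10 minutes". For interferon history and concomitant medication, the Annex 3 flowchart marks the database and not the questionnaire. For newborn data it marks both. The questionnaire in section 9.4.2 takes body measurements from check-ups 2 to 8 only, so size at birth is a database item whose gaps may be filled at interview. Section 9.2 states that the privacy consent signed on joining the support program covers the extract.

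Section 9.1.2 lists among the secondary endpoints "Number and proportion of women discontinuing SC Peginterferon beta-1a or IM Interferon beta-1a therapy during pregnancy", with parallel endpoints for starting and restarting interferon, other therapies used in pregnancy, and child size from birth onward.

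On numbers, section 9.5 gives "n = 202 pregnancy and pregnancy outcome reports for 184 female patients under SC Peginterferon beta-1a". For the intramuscular product its count is "n = 245 pregnancy and pregnancy outcome reports for 199 female patients treated with IM Interferon beta-1a". Of all these pregnancies, 368 ended in a live birth. The section then says "About 290 patient questionnaires are expected to be completed during the telephone interview (80% return rate estimated". The Abstract says "about 310 patient questionnaires are expected to be completed during the telephone interview".

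**The concern.** For endpoints that exist only in the questionnaire, restriction to responders cannot be avoided. For endpoints already in the database it adds selection that the design does not need. A woman must be reachable, willing to take part and the mother of a live-born child before her interferon use in pregnancy is counted.

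The live-birth condition matters most for stopping or starting interferon and for medication during pregnancy, because it selects on an event that follows the behaviour being described. Section 8.1 asks whether and when treatment is stopped in women who become pregnant, which is a wider group than live-birth responders.

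Section 9.9 does not mention this selection. The ENCePP checklist marks selection bias as not applicable in its section 7, yet in its section 12 ticks it as discussed in 9.9. At stake are secondary tables that describe a narrower group than the data allow, with no check on how that group differs from the rest.

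**Working it through.** **Inputs** (section 9.5 unless stated): 202 and 245 pregnancies in 184 and 199 women; 368 live-birth pregnancies; about 290 questionnaires at an 80% return; about 310 questionnaires and about 400 patients in the Abstract. One questionnaire per live-birth pregnancy is assumed, as the 80% of 368 implies.

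1. *The plan's own figure.* 0.80 × 368 = 294.4, against about 290 stated (290/368 = 78.8%). This agrees to rounding.
2. *Full base.* 202 + 245 = 447 pregnancies in 184 + 199 = 383 women.
3. *Excluded by the live-birth condition.* 447 − 368 = 79 pregnancies; 79/447 = 17.7%.
4. *Excluded by the interview condition.* 368 − 290 = 78 live births.
5. *Share left out, by type of endpoint:*

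| Endpoint | Usable base | In the set | Left out |
|---|---|---|---|
| Birth weight, length, head circumference; interferon restart | 368 live births | 290 | 78/368 = 21.2% |
| Interferon stop or start, concomitant medication in pregnancy | 447 pregnancies | 290 | (79 + 78)/447 = 35.1% |
| Check-ups, lactation, other MS therapies, relapses, EDSS | questionnaire only | 290 | not avoidable |

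6. *Sensitivity to the expected return.* At exactly 80% (294.4), the shares are 1 − 294.4/368 = 20.0% and 1 − 294.4/447 = 34.1%. With 310 questionnaires on the same bases they are 15.8% and 30.6%. A return below 80% would raise both.
7. *What selection could do.* The full-group proportion differs from the responder proportion by the share left out times the difference between those left out and those included. The documents do not give that difference. For each 10 percentage points assumed, the shift is 0.351 × 10 = 3.5 points over all pregnancies, or 0.212 × 10 = 2.1 points over live births.
8. *The two questionnaire counts.* On 368 live births, 310 needs a return of 310/368 = 84.2%. At 80% it needs 310/0.80 = 387.5 live births. Scaling to the Abstract's 400 patients gives 294.4 × 400/383 = 307.5, so 310 could be a projection to the data cut-off. The Abstract, however, says that it rests on current data, and nothing links the two figures.

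**The case against.** The strongest case for the plan has four parts.

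- **The interview is where the records are completed and checked.** Section 9.4.2 expects incomplete reports and closes the gaps by telephone. Section 9.8 adds a manual cross-check of lactation and interferon data. This stands: database-only records will be less complete, and 21% and 35% are the most that could be recovered at the expected return. It is a reason to show missing values, for which section 9.7 already provides a row, and not a reason to omit the records.
- **Pregnancies that end early leave less time to stop or start treatment.** A single proportion, or time to discontinuation, over all 447 would mix truncated with full-length pregnancies. This stands and shapes the fix. It does not touch birth size or restart.
- **The scope is declared.** Section 8.3 says openly that the secondary objectives concern a subpopulation. That makes the restriction transparent, but it does not make it necessary for database items.
- **The counts are approximate.** Both questionnaire figures are rounded, and section 9.5 allows for growth until the cut-off. So this is a matter of alignment, not a calculation error.

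A reader might infer more than the documents support:

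- That all these data exist for every pregnancy. Birth size exists only for births.
- That the excluded data are thrown away. Section 9.7 has all obtained data listed, and the primary endpoint uses the full set.
- That stopping and starting go unreported outside the responders. The primary-endpoint subgroups in section 9.7.2 should yield those counts as group sizes for the full set, though not time to discontinuation or medication use.
- That confidence intervals will be about 13% or 24% wider (√(368/290) = 1.13; √(447/290) = 1.24). The protocol plans no intervals. The ratios also assume complete records and independent pregnancies, while 447 pregnancies come from 383 women.

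**Conclusion.** The point holds for a defined group of secondary endpoints. For birth size and interferon restart, up to 21% of live births are left out of the tables. For interferon stop or start and concomitant medication during pregnancy, up to 35% of pregnancies are left out, about half of them (79 of 157) because the pregnancy did not end in a live birth. These shares assume about 290 questionnaires, one per pregnancy, and complete database records. Incomplete records lower what can be recovered.

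The direction and size of any resulting bias cannot be determined from the protocol. The primary endpoint is unaffected, and the questionnaire set is right for items asked only at interview. The analysis sets are stated in the protocol itself, so a different set in the SAP would depart from it; the protocol text should be changed. The 290 and 310 figures need aligning, which is a smaller, separate correction.

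**What to change.** Amend section 8.3, section 9.7.1.2 and the Abstract so that the secondary set follows the data source:

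- **Birth weight, length and head circumference, and interferon restart:** all live births in the primary set.
- **Interferon stop or start, and concomitant medication during pregnancy:** all pregnancies in the primary set, shown overall and separately for live births and other outcomes, with the row for missing values kept.
- **Check-ups, lactation, other MS therapies, relapses and EDSS:** the questionnaire set, as now.
- **Responders against non-responders:** a descriptive table among live births on the variables held for both.

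State the expected number of questionnaires once, in pregnancies, in both the Abstract and section 9.5. On the mid-July 2020 data that is 0.80 × 368 = 294. If about 310 is a projection to the cut-off, say so and give its base.

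No new data collection is needed, since the extract is already planned and consented. The cost is a wording change and a few more tables. Denominators will differ between secondary tables and must be labelled. A footnote should say that database-only records were not completed or cross-checked at interview.
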